2. To identify patient and physician behaviors associated with GERD symptom improvement.

Design and Outcomes

This is a randomized controlled trial to assess the physiologic and behavioral mechanisms associated with augmented medication effects in adult patients with functional GERD-related symptoms.

Subjects will be randomized to receive one of two different semi-scripted visit types – either a “standard visit” modeled after an empathic, conventional primary care evaluation or an “expanded visit” modeled after an integrative medicine consultation. During the visit, we will measure heart rate variability (HRV) and galvanic skin response (GSR) in the patient-provider dyads; in addition, we will video record the interactions for later

analysis of behavioral responses. Subjects will receive a two-month supply of amitriptyline (10 mg/day) or omeprazole (20 mg/day, depending upon the nature of their GERD symptoms), along with instructions for taking it. Following the visit, subjects will complete questions assessing their relationship/rapport with the study provider. Subjects will complete a daily GERD symptom diary during the first and eighth weeks of the study. At the end of the 8-week observation period, they will complete follow-up measures of GERD symptom severity and quality of life.

Interventions and Duration

Subjects will have a single visit with a “study provider,” a physician or nurse practitioner who they have never previously met. Subjects will complete a daily symptom diary for the 1st and 8th weeks following this visit and return for a second study visit in which they will complete questionnaires and be debriefed by a member of the study team.

Sample Size and Population

We plan to enroll 60 subjects with functional GERD, age 24-70 with heartburn symptoms 3 or more days per week. Thirty subjects will be randomized to the expanded visit intervention and 30 subjects will be randomized to the standard visit intervention (1:1 expanded vs. standard randomization). We will also enroll approximately 5-6 physicians or nurse practitioners and stratify randomization by study provider such that each provider will see 10-12 subjects (5-6 expanded visits and 5-6 standard visits).

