3. STUDY DESIGN

Study design: Single-center, single-blind, randomized controlled trial

Primary outcome:

1. Change in the average daily GERD symptom severity score from baseline to the last week of the study in the expanded vs. standard group. GERD symptom severity is based on the sum of scores assessing the severity of daytime heartburn, nighttime heartburn, and acid reflux each on a 0-4 point scale (none, mild, moderate, severe, very severe; higher scores signify worse symptoms).

Secondary outcomes:

1. Ratio of the sum of positive correlations over the sum of negative correlations in GSR (or HRV) across patient-provider encounters for standard vs. expanded visit types and for responders vs. non-responders (those with a 50% or greater improvement in their GERD symptom severity).
2. Absolute change in GSR (or high frequency HRV signal) in patient recordings from the beginning of the study visit to the end of the study visit and correlation with subsequent change in GERD symptom severity.
3. Differences in blinded ratings of 2 minute thin slices of study visit videos from the beginning to the end of the study in supportive global impressions (e.g., engagement, relaxed, patient seems pleased/satisfied) and non-verbal behaviors (e.g., smiling) between standard and expanded visit types and correlation with subsequent change in GERD symptom severity.

Study population:

Men and women age 24-70 with heartburn symptoms 3 or more days per week not responsive to proton pump inhibitors or with known functional heartburn. We will enroll until we reach 60 completing subjects.

Study location:

University of California Davis Medical Center

Length of subject participation: 8 weeks

Length of study enrollment: 2 years

Groups:

- 1) Standard visit (n=30), modeled after an empathic, high quality conventional primary care visit.
- 2) Expanded visit (n=30), modeled after a visit with an integrative medicine provider

Randomization:

The randomization code will be generated by the study statistician as described below (sections 4.3 and 9.2). The study will be single-blinded (study providers and the research team will know what the subject is receiving but the subject will not). Randomization will be stratified based on study provider. We anticipate 5 or 6 providers each seeing 10-12 subjects (5-6 standard visits, 5-6 expanded visits).

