9.2 Sample Size and Randomization

The combined standard deviation (root mean square error) in my pilot fellowship study was 1.5⁶⁴. We are conservatively assuming that this number will likely be larger in this study given the greater number of providers involved. Given 30 subjects in each group (n=60 total), 80% power, a two-sided significance test with alpha = 0.05, the minimal detectable difference (MDD) in GERD symptom severity scores between the standard and expanded groups given the estimated standard deviations (SD) is shown in the adjacent table. These MDD values are similar to those found in my fellowship study⁶⁴ and are clinically meaningful^{86,87}.

Minimal Detectable Difference Between Groups	
SD	MDD
1.5	1.10
2.0	1.47
2.5	1.84

Treatment Assignment Procedures

A randomization scheme will be devised before the start of the study by the study biostatistician who will retain the code and will be responsible for breaking the blind at the end of the study. We do not anticipate a need to break the blind during the study because we are not expecting serious adverse events to occur more frequently in one visit group than another. Randomization will be stratified by provider, with permuted block sizes of 2 and 4 with a goal to have 5-6 providers each see 10-12 subjects. If a provider cannot commit to this many visits, the study biostatistician may need to adjust the randomization scheme and we will consent additional providers.

The study biostatistician will enter the randomization scheme into REDCap and subjects will be randomized immediately prior to the study visit intervention.

If a subject drops out or is unable to complete the study, the statistician may need to rebalance the randomization scheme.

Subjects will be informed of their visit group assignment during the debriefing at the end of the second study visit.

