9.5 Outcomes

A combination of description statistics, pearson correlations, and general linear models (GLM) such as ANCOVA, will be used for analyzing the data.

Assessment	Time Points Collected	Analysis Plan	Section
Demographics, health behaviors, height & weight	Visit 1	Descriptive statistics	9.6
Daily GERD Symptom Diary	Visit 1 & Visit 2	Primary Outcome – ANCOVA analysis adjusting for baseline GERD symptom severity and visit type using follow-up GERD symptoms as the outcome.	9.5.1
GERD-HRQL	Visit 1 & Visit 2	Descriptive statistics and secondary measures of GERD symptom severity in ANCOVA analyses.	9.6
NIH PROMIS GERD			
GSRS			
Current Stress	Visit 1 (both before & after provider visit) & Visit 2	Descriptive statistics and covariate in GLM analyses.	9.6
PSS-10	Visit 1 (before provider visit) & Visit 2	GLM to determine whether perceived stress is a modifying factor for change in GSR and HRV in the context of the visit intervention	9.6
FFI	Visit 1	GLM to determine whether personality is a modifying factor for change in GERD symptoms in the context of the visit intervention	9.6
GSR & HRV	Visit 1	Secondary Outcome – GLM assessing change in GERD symptom severity and physiologic concordance in patient-provider dyads	9.5.1
Video Recording	Visit 1	Secondary Outcomes - GLM to compare the frequency of supportive provider behaviors between the standard and expanded visit groups and responders vs. non-responders (those with a 50% or greater improvement in GERD symptoms).	9.5.2
Impressions of the Study Physician	Visit 1, post-intervention	GLM to determine whether empathy and the patient-provider connection modify change in GERD symptoms in the context of the visit intervention	9.6
CARE			
HEAL Patient-Provider Connection			

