9.5.2 Secondary Outcomes

1. To analyze physiologic synchrony in GSR, first, an average slope of the GSR will be calculated in the patient and provider recordings in moving 5 second windows, offset by 1 second. Next, Pearson correlations with lag zero will be calculated over successive 15 second windows between time-locked patient and provider GSR slope values. Then, a single session index will be calculated from the ratio of the sum of the positive correlations across the entire visit divided by the sum of the absolute value of the negative correlations across the entire visit. To reduce skew, the natural logarithm of the index will be calculated. Thus, an index value of zero reflects equal positive and negative correlations, a value greater than zero reflects more concordance in GSR than not, while a value less than zero reflects less concordance in the dyad (less than 50%)⁸². These index values will be used in GLM analyses with GERD symptom severity and/or correlated with visit type.

We will also perform similar analyses on the HRV data – comparing variation in the beat-to-beat intervals over short segments of time and calculating Pearson correlation coefficients for time-locked patient and provider data for these intervals.

2. We will calculate absolute changes in both GSR and also high frequency HRV within study subjects from the beginning to the end of the study visit. We will assess the Pearson correlation between these changes and reported changes in GERD symptom severity. We will also look at absolute levels of GSR and HRV at the end of the study visit and compare those values with changes in GERD symptom severity in GLM models. As an exploratory analysis, I will test whether changes in GSR and HRV are a function of baseline perceived stress and if that relationship differs between the standard and expanded visit interventions.
3. To analyze study visit videos, 2 minute thin slices of each video at three time points (beginning, middle, and end of study visits) will be analyzed by trained and blinded coders, for the presence of 1) micro-level non-verbal supportive behaviors (e.g., gazes, smiles, nods, gestures – measured as absolute number or

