length of time) as well as 2) macro-level impression ratings of the interaction (e.g., engagement, friendliness, relaxed, empathic, reciprocity – measured on a 1-9 scale). The PI will meet weekly with the coders to review findings and resolve areas of disagreement until greater than 70% concordance is achieved between coders using Cronbach's alpha. Each of these variables will be assessed in a GLM examining time, visit type, and time x visit type effects. We will also calculate the Pearson correlation coefficient for each variable relative to improvement in GERD symptoms and construct a GLM examining patient and provider smiling as a predictor of improvement in GERD symptoms. Other models may also be constructed based on the results of the initial video analyses.

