9.6 Data Analyses

We will perform descriptive statistics on the sample demographics similar to our prior paper⁶⁴ including age, gender, race, ethnicity, body mass index (BMI), smoking status, and current medication use for GERD symptoms. We will also assess whether perceived stress, perceived empathy (both patient and provider), personality type (five factor inventory), or demographic factors modify improvement in GERD symptoms using generalized linear models. We will use the GERD-HRQL, NIH PROMIS GERD, and GSRS as adjunct/corroborating measures of GERD symptom severity. Blood samples will be processed and stored at - 80°C for later omics-based analyses that will be the subject of a future grant/study.

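### The video model names no error term for three slices from the same visit; fitted as an ordinary GLM, its visit-type test would reject too often

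*Combined protocol and SAP*

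**What the plan says.** Section 9.5.2 of the combined protocol and SAP has blinded coders score "2 minute thin slices of each video at three time points (beginning, middle, and end of study visits"). The scored items are small non-verbal behaviours, recorded as counts or durations, and global impressions on a 1-9 scale. The model is given in one sentence: "Each of these variables will be assessed in a GLM examining time, visit type, and time x visit type effects".

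The meaning of GLM has to be gathered from other places. Section 9.5 says that "general linear models (GLM) such as ANCOVA, will be used for analyzing the data". The video row of the table in that section says only "GLM to compare the frequency of supportive provider behaviors between the standard and expanded visit groups", and adds a comparison of responders with non-responders. Section 9.6 uses a different term, proposing to test whether "demographic factors modify improvement in GERD symptoms using generalized linear models".

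No section names a repeated-measures model, a mixed model, a visit or dyad effect, a covariance structure or clustered errors for the slices. None says that the slices will be treated as independent. Provider is the randomization stratum (sections 4.3, 6.2.3 and 9.2) but is not among the effects listed for this model.

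**The concern.** Visit type is assigned once per visit, so the comparison of expanded with standard visits carries the information of 60 visits. A model with a time factor must take in all three slices from each visit, and these share a patient, a provider and a conversation. If nothing in the model ties them together, the visit-type contrast is judged against slice-level residual variation on 180 rows. Its standard error is then too small whenever slices from one visit resemble each other.

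That contrast is the test of secondary hypothesis 4 (section 9.1), which says that providers show more supportive behaviour in expanded visits. It is repeated for each coded variable. The same fit errs in the opposite direction for time and for time by visit type. These are within-visit comparisons, and they would be judged against an error that wrongly includes between-visit variation. A real difference in how behaviour develops over the visit would be harder to detect.

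**Working it through.** **The plan's own figure.** The documents give no operating characteristics for the video analysis. The only sample-size figure is for the primary outcome (section 9.2): "Given 30 subjects in each group (n=60 total), 80% power, a two-sided significance test with alpha = 0.05", with minimal detectable differences of 1.10, 1.47 and 1.84 for SDs of 1.5, 2.0 and 2.5. A two-sample t-test on 58 df (noncentral t) gives 1.103, 1.471 and 1.839, so that table reproduces. The normal approximation, SD × √(2/30) × (1.960 + 0.842), gives 1.085, 1.447 and 1.808.

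**Inputs for the video model.**
- Visits: 30 per arm, from "1:1 expanded vs. standard randomization" (Précis) and "We will enroll until we reach 60 completing subjects" (section 3).
- Slices per visit: 3 (section 9.5.2), so 60 × 3 = 180 rows. With 6 cell means, the residual df are 180 − 6 = 174.
- Alpha: two-sided 0.05, carried over from the primary outcome because none is stated for the video outcomes.
- Within-visit correlation ρ: not in the documents. A range of 0.1 to 0.7 is assumed.
- Further assumptions: normal outcomes, equal correlation between slices, no missing slices.

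**Visit-type test, slices fitted as independent rows.** The true variance of the visit-type contrast is 1 + (3 − 1)ρ = 1 + 2ρ times the variance the model assumes. Hence type I error = 2 × [1 − Φ(1.96/√(1 + 2ρ))].

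**Time and interaction tests, same fit.** The true variance of a within-visit contrast is (1 − ρ) times the variance the model assumes. Each test has 2 df, so type I error is approximately P(χ² on 2 df > 5.99/(1 − ρ)) = 0.05^(1/(1 − ρ)).

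**Check by simulation.** 20,000 null trials per ρ, with F tests on 174 residual df. The comparator is a t-test on each visit's mean of three slices, which equals the between-visit test of a balanced repeated-measures model.

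| ρ | 1 + 2ρ | 1.96/√(1 + 2ρ) | Visit type, formula | Visit type, simulated | Time × visit type, formula | Time × visit type, simulated | Visit type, between-visit error, simulated |
|---|---|---|---|---|---|---|---|
| 0 | 1.0 | 1.96 | 0.050 | 0.051 | 0.050 | 0.051 | 0.051 |
| 0.1 | 1.2 | 1.79 | 0.074 | 0.073 | 0.036 | 0.037 | 0.051 |
| 0.3 | 1.6 | 1.55 | 0.121 | 0.121 | 0.014 | 0.013 | 0.052 |
| 0.5 | 2.0 | 1.39 | 0.166 | 0.163 | 0.0025 | 0.003 | 0.049 |
| 0.7 | 2.4 | 1.27 | 0.206 | 0.207 | 0.00005 | 0.0001 | 0.050 |

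The simulated time test behaves like the interaction: 0.036, 0.016, 0.003 and 0.0001 at ρ = 0.1, 0.3, 0.5 and 0.7. With a between-visit error term, the visit-type test stays between 0.049 and 0.052 at every ρ tried from 0 to 0.9.

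**The case against.** The strongest reply is that silence is not a decision. A GLM with time, visit type and their interaction is also how one would describe a design with one within-visit and one between-visit factor, and standard practice fits that as a repeated-measures GLM. ANCOVA is offered as an example and not as a limit, and the term GLM is used loosely across sections 9.5 and 9.6. This stands. A reader might infer that the plan treats the 180 slices as independent, or that its visit-type test is already far too liberal. The documents do not support that. They leave the error term open.

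Three further points also stand:
- **The affected test depends on the reading.** Secondary outcome 3 (sections 3 and 9.1) can be read as change across the visit by arm, which is the interaction. Under the naive fit that test loses power and does not gain false positives. The video row in section 9.5 mentions no time factor, so a comparison of visit-level values would also fit it.
- **The size rests on an assumed correlation.** It need not be the same for nods, gaze time and 1-9 ratings. It cannot be said that p-values would be too small for every coded variable to the same degree.
- **Provider is not the cause.** Each provider delivers both visit types in near-equal numbers, so leaving provider out does not produce this inflation. A mixed model that includes provider is not the same model as a repeated-measures GLM without it.

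None of this removes the point. Two analysts following the text could fit models with type I errors of about 5% and about 7% to 21%, and section 9.5.2 also allows further models after the first video results are seen.

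**Conclusion.** The concern holds conditionally. The plan lists the effects for a model of three slices per visit and names neither an error term for the visit nor the stratification factor. Fitting the listed effects literally gives the visit-type test a type I error of about 7%, 12%, 17% and 21% at ρ = 0.1, 0.3, 0.5 and 0.7, against a nominal 5%. The time and interaction tests fall well below 5%. A repeated-measures fit avoids both errors. The figures assume normal outcomes, equal correlation between slices, complete slices and a two-sided 0.05 level, and the range for ρ is not from the documents.

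This is a secondary, mechanistic analysis. The primary ANCOVA (section 9.5.1) uses one follow-up value per subject and is not touched. The point should be settled before the video data are analysed, because the plan currently leaves open a choice that affects the error rate.

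**What to change.** Replace the model sentence in section 9.5.2 with one that fixes the error structure. For each coded variable, fit time, visit type and time by visit type with a random intercept for visit. Alternatively, use a repeated-measures GLM with visit as the subject. In either case, test visit type against between-visit variation. For behaviours recorded as counts, allow a generalized version of the same model with the same visit term.

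Add provider as a fixed effect, because randomization is stratified by provider and the outcome is largely provider behaviour. This is a separate gain in precision and does not cure the inflation. With 5 or 6 providers it uses 4 or 5 of the 60 − 2 = 58 between-visit degrees of freedom, leaving 54 or 53. Use one term consistently, general or generalized linear model, in sections 9.5 and 9.6.

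The cost is two or three sentences in the plan and no new data. Compared with an independent-rows fit, intervals for visit type would be wider and those for the within-visit effects narrower. If a repeated-measures fit was always intended, only the wording and the provider term change.

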9.5.1 Primary Outcome

1. Change in the average daily GERD symptom severity score from baseline to the last week of the study in the expanded vs. standard group. GERD symptom severity is based on the sum of scores assessing the severity of daytime heartburn, nighttime heartburn, and acid reflux each on a 0-4 point scale (none, mild, moderate, severe, very severe; higher scores signify worse symptoms). We will use ANCOVA for the primary analysis, adjusting for baseline GERD symptom severity and visit type assignment using the 8 week follow-up GERD symptom severity as the outcome. Potential moderators that will be assessed in exploratory analyses will include gender (both patient and provider), race, visit length, patient stress, personality type, and perceived connection with/empathy of the provider.

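### In 9.5.2 the symptom analyses for concordance and provider behaviours do not name visit type, so the pooled association alone cannot support the mechanism aim

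*Combined protocol and SAP*

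**What the plan says.** Section 9.5.2 describes these tests linking the visit to later symptoms:

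- GSR and high-frequency HRV change during the visit: "We will assess the Pearson correlation between these changes and reported changes in GERD symptom severity".
- End-of-visit GSR and HRV levels: the plan will "compare those values with changes in GERD symptom severity in GLM models", with no covariates listed.
- Concordance (the synchrony index): "These index values will be used in GLM analyses with GERD symptom severity and/or correlated with visit type". Visit type appears here as a separate correlate, not as a term in the symptom model.
- Video variables: "We will also calculate the Pearson correlation coefficient for each variable relative to improvement in GERD symptoms". The plan will also "construct a GLM examining patient and provider smiling as a predictor of improvement in GERD symptoms".

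Visit type is named in two other places in 9.5.2: the model with a video variable as outcome, and an exploratory test of stress against GSR and HRV. Neither contains symptoms.

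The table in 9.5 describes the GSR/HRV analysis as "GLM assessing change in GERD symptom severity and physiologic concordance in patient-provider dyads" and points it to 9.5.1. For current stress it says "Descriptive statistics and covariate in GLM analyses". Its video row describes a GLM comparing supportive provider behaviours between visit groups and between responders and non-responders. Secondary outcome 1 (sections 3 and 9.1) does the same for the concordance ratio. Neither says whether the two factors enter one model or are two separate comparisons.

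The primary ANCOVA in 9.5.1 is explicit: "adjusting for baseline GERD symptom severity and visit type assignment using the 8 week follow-up GERD symptom severity as the outcome".

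**The concern.** The hypotheses in 9.1 predict that the expanded visit improves symptoms (primary), raises concordance (secondary 1) and produces more patient-centred provider behaviour (secondary 4). If the first prediction holds together with either of the others, visit type shifts both sides of the correlation. Pooling the two arms then yields an association even when, inside each arm, dyads with more concordance or more supportive behaviour do no better than the rest.

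The Précis (Design and Outcomes) and section 2.2 present these analyses as evidence on mechanism. The planned arm comparisons show whether the marker and the symptoms each move. They do not show whether a link remains once visit type is held fixed. A feature that merely accompanies the longer visit could therefore be taken for an active ingredient.

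The point bears on concordance and provider behaviours. The plan predicts no arm difference in GSR/HRV change or in patient smiling. If visit type does not move a marker, no correlation is induced.

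**Working it through.** **Inputs from the plan (9.1, 9.2).** 30 per arm, 1:1 allocation, two-sided alpha 0.05, 80% power, SD 1.5, 2.0 or 2.5, minimal detectable difference (MDD) 1.10, 1.47 or 1.84.

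**The plan's own figure.** A two-sample t-test with 58 df has 80% power at a standardized difference of 0.7356. This gives 0.7356 × 1.5 = 1.103, × 2.0 = 1.471 and × 2.5 = 1.839, so the MDD table reproduces. Section 9.2 calls these MDDs similar to the pilot findings, so 0.7356 SD is used as the symptom effect *dy*, with half of it (0.3678) as a weaker case.

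**Assumed.** The documents give no visit-type effect on any marker. The values *dx* = 0.3, 0.5 and 0.8 within-arm SD are assumptions shown as a range. Clustering by provider is ignored.

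**Induced correlation.** With no link inside either arm and 1:1 allocation, the pooled covariance is dx·dy/4 and the pooled variances are 1 + dx²/4 and 1 + dy²/4. Hence

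r = (dx·dy/4) / √[(1 + dx²/4)(1 + dy²/4)].

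Example: dx = 0.5 and dy = 0.7356 give 0.0920 / √(1.0625 × 1.1353) = 0.084.

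**Rejection rates.** 40,000 simulated trials of n = 60 per cell. The pooled Pearson test (58 df) is compared with the partial correlation given visit type (57 df).

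| dy | dx | induced r | pooled test | adjusted test |
|---|---|---|---|---|
| 0.7356 | 0 | 0 | 5.0% | 5.0% |
| 0.7356 | 0.3 | 0.051 | 6.7% | 5.1% |
| 0.7356 | 0.5 | 0.084 | 9.7% | 4.9% |
| 0.7356 | 0.8 | 0.128 | 16.5% | 5.1% |
| 0.3678 | 0 | 0 | 5.0% | 5.1% |
| 0.3678 | 0.3 | 0.027 | 5.6% | 5.0% |
| 0.3678 | 0.5 | 0.044 | 6.2% | 4.8% |
| 0.3678 | 0.8 | 0.067 | 8.0% | 5.1% |

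For scale, the critical |r| at n = 60 is 0.254.

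**Change scores.** Section 9.2 describes the pilot SD as a root mean square error. If it is a baseline-adjusted residual SD, the effect on the change score is somewhat smaller. With an assumed pre-post correlation of 0.3, 0.5 or 0.7 (20,000 trials), the pooled test rejects in 8–9% of trials at dx = 0.5 and 12–15% at dx = 0.8. The regression of 8-week severity on marker, visit type and baseline stays at about 5%.

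**Cost of adjusting.** By Fisher's z, the detectable r at 80% power is tanh[(1.960 + 0.842)/√(57 − k)] with k covariates: 0.355 (k = 0), 0.358 (k = 1) and 0.361 (k = 2). If the marker carries the whole visit effect and the within-arm r is 0.36, the pooled test has 84%, 87% and 95% power at marker effects of 0.5, 0.8 and 1.5 SD. The test adjusted for visit type has about 81% in each case.

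**The case against.** The strongest reply is that the planned tests match the stated hypotheses. Secondary hypotheses 2 and 5 ask only for a correlation or an association, and the pooled correlation is a valid total association. When visit type moves both variables that correlation truly is non-zero, so the excess over 5% is not type I error of the planned test. This stands. A reader might infer that the tests are invalid or that the plan intends to report a pooled correlation as mediation; the documents support neither.

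Second, visit type is unnamed in the GLMs, not excluded. Section 9.5 allows models such as ANCOVA, 9.5.2 leaves room for further models, and the video row and secondary outcome 1 mention visit type beside responder status. This stands for the GLMs, where the text is ambiguous. It does not help the Pearson correlations, which carry no covariates. Further models chosen after seeing the video results are not pre-specified either.

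Third, the table's pointer of the GSR/HRV row to 9.5.1 might be read as adopting the primary model, or as showing that the plan contradicts itself. It is probably clerical and supports neither reading.

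Fourth, adjustment removes part of the signal if the marker mediates the visit effect, and it does not prove mechanism, because the marker is not randomized. Both are true. That is a reason to show both results, not to omit the adjusted one.

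**Conclusion.** The point holds as a minor one, for concordance and provider behaviours (provider smiling included). For these the plan itself predicts movement with visit type, and the pooled association cannot separate a shared visit-type effect from a link inside visit type. With no such link, the pooled test rejects in about 6% to 17% of trials over the assumed range, against 5% adjusted. The top of that range needs an assumed 0.8 SD marker effect together with the full MDD-sized symptom effect. Larger marker effects would give larger figures, but the documents offer no basis for them.

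A reader might extend the criticism to every marker-symptom test in 9.5.2. The documents do not support that for GSR/HRV change or patient smiling, where no arm difference is predicted. Nothing here touches the primary analysis.

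**What to change.** Keep the pooled correlations. For concordance and provider behaviours, including provider smiling, pre-specify beside them a regression of 8-week severity on the marker with visit type and baseline severity, the form already used in 9.5.1. Report the marker coefficient or partial correlation with its confidence interval. For the responder comparison in the video row of the 9.5 table, add visit type to the GLM, and say whether visit type and responder status in secondary outcome 1 form one model or two. Base any statement about a link beyond the visit-type effect on the adjusted result. The same model may be shown for GSR/HRV change and patient smiling for consistency. Correct or explain the table's pointer of the GSR/HRV row to 9.5.1.

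The cost is SAP wording and a little more analysis, with no new data. The detectable r rises by 0.006 (0.355 to 0.361). Under full mediation the adjusted test gives up about 3 to 14 percentage points of power (81% against 84–95%).
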